6.2.2.5. Regulatory Reporting Requirements for SAEs

Prompt notification by the investigator to GSK or designee of SAEs and non-serious AEs related to study treatment (even for non- interventional post-marketing studies) is essential so that legal obligations and ethical responsibilities towards the safety of subjects and the safety of a product under clinical investigation are met.

GSK has a legal responsibility to notify both the local regulatory authority and other regulatory agencies about the safety of a product under clinical investigation. GSK will comply with country specific regulatory requirements relating to safety reporting to the regulatory authority, Institutional Review Board (IRB)/Independent Ethics Committee (IEC) and investigators.

Investigator safety reports are prepared for suspected unexpected serious adverse reactions according to local regulatory requirements and GSK policy and are forwarded to investigators as necessary.

An investigator who receives an investigator safety report describing a SAE(s) or other specific safety information (e.g., summary or listing of SAEs) from GSK will file it with the IB and will notify the IRB/IEC, if appropriate according to local requirements.

6.2.3. Adverse Events of Special Interest

The investigator or site staff will be responsible for detecting, documenting and reporting events the following AEs of special interest:

- Development of thyroid cancer
- Haematologic malignancy
- Pancreatic cancer
- Pancreatitis
- Injection site reactions
- Immunological reactions (e.g., drug hypersensitivity reactions involving anaphylaxis/anaphylactoid reactions, acute bronchoconstriction, angioedema, and/or acute urticaria)
- Severe hypoglycaemia events (which includes all events meeting the definition of SAEs [Appendix 5](#))
- Hepatic events
- Hepatic enzyme elevations (including GGT)
- Serious GI events
- Appendicitis
- Atrial fibrillation/flutter
- Pneumonia
- Worsening renal function
- Diabetic retinopathy

The results of any investigation should be recorded in the relevant sections of the subjects' eCRFs. In addition, for thyroid, pancreas or haematological malignancies a copy of the histopathology report and a discharge summary if the subject was admitted, or any available case summary (e.g. clinic letter), is to be provided to the Sponsor, if available.

Subjects with treatment emergent thyroid nodules should be referred to a specialist for evaluation in accordance with local treatment guidelines. In subjects where a treatment emergent thyroid nodule is identified, if serum calcitonin is measured at the discretion of the Investigator (e.g., per local guidelines) and found to be >100 ng/L this should prompt

further investigation for MTC and potential interruption or discontinuation of investigational product until diagnosis has been resolved. If MTC or other thyroid C-cell neoplasia is diagnosed, albiglutide will be discontinued.

A Pancreatitis Adjudication Committee composed of independent specialists in gastroenterology will review all cases of possible pancreatitis.

Subjects should also be closely monitored for signs of potential allergic or drug hypersensitivity reactions including anaphylaxis, angioedema, generalized urticaria, and other potential manifestations of systemic allergic or drug hypersensitivity reactions. A serum sample should be taken as soon as possible after any such event in order to measure antibody to the drug. Instructions for sample processing are in the SRM. These events should be reported as AEs or SAEs based on the clinical evaluation of the subject. The reactions should be followed to completion as typical for any AE or SAE. Subjects with allergic or drug hypersensitivity reactions that are considered by the investigator to be attributable to investigational product or without a likely alternative aetiology should have investigational product withdrawn and not re-introduced.

Episodes of severe hypoglycaemia will be recorded according to subject report. Severe hypoglycaemic incidents will be defined as those episodes of hypoglycaemic symptoms for which the subject required assistance from another person and from which the subject recovered promptly after oral carbohydrate, intravenous glucose, glucagon administration or other resuscitative actions (definition per ADA Workgroup on Hypoglycaemia [Seaquist, 2013]). Additionally, all episodes of hypoglycaemic symptoms which in the investigator's opinion meet the definition of a SAE (defined in [Appendix 5](#)) will be included as severe hypoglycaemic episodes. During this study, if a subject's eGFR approaches 30mL/min/1.73m² closer monitoring of renal function is considered prudent, according to standard clinical practice. If eGRF is <15mL/min//1.73m² follow the procedure set out in Section [4.4.4](#).

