Immunogenicity. Hypersensitivity reactions are of potential concern with any injected protein and were reported rarely in the Phase III programme. In the Phase III programme one subject (anti-albiglutide antibody negative) developed rash, itching and dyspnoea. Subjects with known allergy to any GLP-1 receptor agonist or excipients of albiglutide are excluded from the study. Subjects will be informed of the symptoms of severe hypersensitivity or allergy and be advised to seek medical assistance immediately. In the Phase III programme approximately 5% of subjects developed anti-albiglutide antibodies. Subjects who tested positive for anti-albiglutide antibodies experienced a similar glycaemic response (HbA1c and fasting plasma glucose) to those who did not test positive for antibodies. Other than injection site reactions (see below), the overall safety profile appeared similar among the subset of subjects who did and those who did not test positive for anti-albiglutide antibodies. Anti-albiglutide antibody formation is not expected to impact the overall safety of albiglutide treatment and therefore will not be measure routinely in this study.

Injection site reactions. Albiglutide injections may cause rash, erythema or itching and/or other reactions at the site of injection. . Subjects will be advised that when injecting in the same region, to use a different injection site each week. In the Phase III program, most subjects with injection site reactions did not test positive for anti-albiglutide antibodies. However, injection site reactions were reported more frequently among those who did test positive for anti-albiglutide antibodies (41% of the antidrug antibody positive subjects reported one or more injection site reactions) than among those who were consistently antibody negative (14% of the antidrug antibody negative subjects reported one or more injection site reactions) .

Other adverse reactions (e.g. pneumonia, atrial fibrillation/flutter, and appendicitis). In the Phase III programme in type 2 diabetes, other possible albiglutide related adverse reactions were identified. These events occurred at a cumulative incidence <3% in studies up to 3 years in duration. These events were reported more frequently with albiglutide than comparators.

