4.4.2. Reasons for Discontinuation of Investigational Product

Any subject experiencing the following will be required to discontinue investigational product:

- AE:
 - Pancreatitis, acute or chronic.
 - Pancreatic cancer.
 - MTC or other thyroid C-cell neoplasia. In subjects where a treatment emergent thyroid nodule is identified, if serum calcitonin is measured at the discretion of the Investigator (e.g., per local guidelines) and found to be >100 ng/L this should prompt further investigation for MTC and potential interruption or discontinuation of investigational product until diagnosis has been resolved.

- Liver chemistry abnormalities exceeding the threshold criteria outlined in Section 4.4.3
- Severe allergic/hypersensitivity reactions that are considered by the investigator to be attributable to investigational product or without a likely alternative aetiology.
- Other AE which, in the opinion of the investigator precludes continuation of dosing.
- eGFR<15ml/min/1.73m² (Section 4.4.4) or the need for renal replacement therapy.
- Subject becomes pregnant during the study.
- Need for chronic use of a prohibited concomitant medication (Section 5.6.2)
- Decision by subject or proxy.
- Sponsor terminated study.
- Investigator site closed and subject was unable to transfer to another investigative site.

[figure not shown]
If investigational product is discontinued, the subject should continue in the study and be followed until the final study visit as detailed in Section 4.5.

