4.4.3. Liver Chemistry Stopping Criteria

Liver chemistry stopping and increased monitoring criteria have been designed to assure subject safety and evaluate liver event aetiology (in alignment with the FDA premarketing clinical liver safety guidance).

[figure not shown]
<http://www.fda.gov/downloads/Drugs/GuidanceComplianceRegulatoryInformation/Guidances/UCM174090.pdf>

Phase III-IV Liver Chemistry Stopping and Increased Monitoring Algorithm

Liver safety required actions and follow up assessments section can be found in [Appendix 3](#).

Phase III-IV Liver Chemistry Increased Monitoring Algorithm with Continued Therapy for ALT $\geq 3xULN$ but $< 8xULN$

Liver Safety Required Actions and Follow up Assessments Section can be found in [Appendix 3](#).

Drug re-challenge following drug induced liver injury is not allowed.

Restart may be considered if GSK Medical Governance approval is granted (see [Appendix 4](#) for details). Restart refers to resuming study treatment following liver stopping events in which there is a clear underlying cause (other than DILI) of the liver event (e.g. biliary obstruction, pancreatic events, hypotension, acute viral hepatitis). Furthermore, there should be no evidence of alcoholic hepatitis or hypersensitivity, and the study treatment should not be associated with human leukocyte antigen (HLA) markers of liver injury.

4.4.4. eGFR Stopping Criteria

A baseline eGFR $\geq 30\text{mL}/\text{min}/1.73\text{m}^2$ is a requirement for entering the study. Subjects can continue to take investigational product if functioning well as long as eGFR is $\geq 15\text{mL}/\text{min}/1.73\text{m}^2$.

During this study, if a subject's eGFR approaches $30\text{mL}/\text{min}/1.73\text{m}^2$ closer monitoring of renal function is considered prudent, according to standard clinical practice. Particular

care should be taken to monitor renal function in subjects with renal impairment reporting severe adverse GI events. If eGRF is $<15\text{mL}/\text{min}/1.73\text{m}^2$ and considered irreversible based on consecutive measurements the investigational product should be discontinued, the subject continue in the study and be followed until the final study visit.

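### The mandatory stopping list in Section 4.4.2 covers only severe allergic reactions, while Section 6.2.3 calls for permanent withdrawal after attributable systemic reactions of any severity

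*Protocol*

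**What the plan says.** Section 4.4.2 opens its list with "Any subject experiencing the following will be required to discontinue investigational product". The allergy entry reads "Severe allergic/hypersensitivity reactions that are considered by the investigator to be attributable to investigational product", and goes on to include reactions with no likely alternative aetiology. It does not mention re-introduction and does not refer to Section 6.2.3.

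Section 6.2.3 asks for close monitoring for anaphylaxis, angioedema, generalised urticaria and other systemic manifestations, and for a serum sample for antibody testing after such an event. It then gives a rule for "Subjects with allergic or drug hypersensitivity reactions that are considered by the investigator to be attributable to investigational product". The rule also takes in reactions for which no other cause is likely, and its instruction is that all these subjects "should have investigational product withdrawn and not re-introduced". The special-interest list in the same section names "Immunological reactions (e.g., drug hypersensitivity reactions involving anaphylaxis/anaphylactoid reactions, acute bronchoconstriction, angioedema, and/or acute urticaria") with no severity qualifier.

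Section 4.4.1 says that a subject who chooses to stop should first be counselled to consider a temporary stop, unless the reason is on the 4.4.2 list.

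Appendix 5 (Section 11.5.4) grades an event as severe when it prevents normal everyday activities, and as moderate when it interferes with them.

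**The concern.** Two sections govern the same clinical event with the same causality test but different thresholds. The narrower threshold is in the section a site would open to decide whether dosing must stop, and it carries the stronger verb (required). The broader rule is in the special-interest reporting section and says should. A site working from the stopping list could keep a subject on drug after a moderate systemic reaction it attributes to the product, or could agree a pause and then resume.

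The product is an injected protein, and Section 3.4.1.1 acknowledges the hypersensitivity concern. Section 5.7 gives a half-life of about 5 days, with therapeutic concentrations persisting for 3 to 4 weeks after stopping, so a mistaken further dose cannot be quickly undone. Exclusion criterion 8 keeps out anyone with a known allergy to a GLP-1 receptor agonist or to the excipients, at any severity. A subject who develops such an allergy on study can thus be held to a looser standard than one who arrives with it.

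**Working it through.** There is no figure to reproduce; the check is a comparison of texts.

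**1. The two rules side by side**

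| Feature | Section 4.4.2 | Section 6.2.3 |
|---|---|---|
| Causality test | Attributable, or no likely alternative aetiology | The same |
| Severity | Severe only | No limit |
| Strength | Required | Should |
| Re-introduction | Silent | Ruled out |
| Link to the other section for allergy | None | None |

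**2. A test case.** Take generalised urticaria or angioedema that the investigator attributes to the product and grades moderate under Appendix 5.
- Section 6.2.3: withdraw, and do not re-introduce.
- Section 4.4.2, allergy entry: does not apply, because the event is not severe.
- Section 4.4.2, entry for other adverse events: applies only if the investigator judges that dosing is precluded, so it permits stopping without requiring it.
- Section 4.4.2, entry for decision by subject or proxy: covers a subject who chooses to stop, but does not require the site to act.

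**3. What Section 4.4.1 then does.** If this subject asks to stop, the allergy entry does not exempt the case from the counselling step. The entry for the subject's own decision could be read as exempting it, but on that reading every subject who chooses to stop would be exempt and the counselling instruction would have no effect. The natural reading is that the site proposes a temporary stop, with resumption in view. Section 3.3 pulls the same way, since it asks for every effort to keep subjects on assigned medication.

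**4. Does being on the 4.4.2 list imply a permanent stop?** Not by itself. Liver stops can be restarted with sponsor approval (Section 4.4.3), and a reversible fall in eGFR leads to a temporary stop (Section 4.4.4). The liver section does state one ban openly: "Drug re-challenge following drug induced liver injury is not allowed". For allergy, the ban appears only in 6.2.3.

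**5. Signs that the difference was not planned.** The calcitonin rule appears in both sections, each ending with "further investigation for MTC and potential interruption or discontinuation of investigational product until diagnosis has been resolved", so on at least one topic they were written to match. The special-interest list in 6.2.3 qualifies hypoglycaemia as severe and gastrointestinal events as serious, but leaves immunological reactions unqualified. This is suggestive rather than conclusive: that list defines what is collected, and the thyroid match says nothing directly about allergy.

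**6. Version.** The full text shown for both sections is that of the original protocol and of Amendment 1, and it agrees on these points. The main body of Amendment 2 is not shown. Its change list in Section 11.9.2 names no change to either passage, so persistence is inferred from that list.

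**The case against.** The strongest reply is that nothing here orders a site to do the wrong thing. A site handling an immunological reaction has to use Section 6.2.3 to report it and to take the antibody sample, and the withdrawal instruction is in that same paragraph. Section 3.1 allows no waivers except for immediate safety concerns, so 6.2.3 also binds. This stands: a site that follows 6.2.3 acts correctly.

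A tiered reading is also possible, with mandatory stopping for severe reactions and recommended withdrawal for the wider group. It is coherent on severity, but the protocol does not set it out, and it does not explain why 4.4.1 should direct the milder group towards a pause when 6.2.3 advises against re-introduction.

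A reader might infer that the two sections conflict on restart. The documents do not support that. Section 4.4.2 is silent and gives no route back for allergy, whereas the liver and eGFR provisions state theirs. Section 4.4.1 also exempts listed reasons from the temporary-stop counselling, which points towards permanence for severe reactions. The list leaves details elsewhere in other cases: its pancreatitis entry carries no restart ban, and Section 3.4.1.1 supplies it. The missing wording on re-introduction is therefore a secondary point.

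A reader might also count injection site reactions as affected subjects. That is not supported either. Sections 3.4.1.1 and 6.2.3 list them separately from immunological reactions, and the paragraph at issue concerns systemic reactions.

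**Conclusion.** The point holds as a mismatch in scope: the mandatory list omits non-severe attributable systemic reactions for which the protocol elsewhere says to withdraw permanently, and 4.4.1 can steer those subjects towards a pause. It should be corrected for patient safety and for consistent handling across sites.

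The number affected is probably small. Section 3.4.1.1 says only that hypersensitivity reactions were rarely reported in Phase III, and no count of non-severe systemic reactions is given, so no rate can be computed.

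A reader might suppose that the primary result is at risk. It is not: the primary analysis is by intention to treat, and subjects are followed after stopping product (Sections 4.4 and 4.5).

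The conclusion assumes that the 6.2.3 sentence refers to the systemic reactions described in its own paragraph, that sites use the Appendix 5 grading to decide what is severe, and that Amendment 2 left both passages unchanged.

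**What to change.** In Section 4.4.2, replace the allergy entry with one that covers systemic allergic or hypersensitivity reactions of any severity, and any severe allergic reaction, that the investigator attributes to investigational product or for which no other cause is likely. Add that product is not to be re-introduced, with a reference to Section 6.2.3. This keeps severe reactions that are not systemic on the mandatory list, and takes the milder systemic reactions out of the temporary-stop counselling in 4.4.1.

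In Section 6.2.3, refer back to 4.4.2 and state that isolated, non-severe injection site reactions are not covered. That line is needed because Section 3.4.1.1 notes that "Albiglutide injections may cause rash, erythema or itching and/or other reactions at the site of injection", and some sites might otherwise treat these as allergic.

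The cost is one line in each of two sections in a protocol amendment, and a few more discontinuations. The change also turns a recommendation into a requirement for the milder systemic reactions, which the sponsor should adopt knowingly.

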6.2.4. Clinically Important Microvascular Events

Clinically important microvascular events are defined as the following: need for renal transplant or dialysis, new diabetes-related blindness, and procedures (laser photocoagulation or anti-vascular endothelial growth factor treatment or vitrectomy for diabetic retinopathy/eye disease). Clinically important microvascular events will be reported as recorded in the eCRF by the investigator without adjudication.

The AEs associated with the above outcomes or treatments should be reported separately as an AE or SAE according to the definitions in [Appendix 5](#).

6.2.5. Pregnancy

- If a subject becomes pregnant during the study they should discontinue Investigational Product.
- Details of all pregnancies in female subjects will be collected after the start of dosing and until the end of the Post-treatment Follow-up Period.

- If a pregnancy is reported then the investigator should inform GSK within 2 weeks of learning of the pregnancy and should follow the procedures outlined in [Appendix 6](#).

6.2.6. Clinical Laboratory Assessments

All protocol required laboratory assessments must be conducted in accordance with the Laboratory Manual, and Protocol Time and Events Schedule ([Table 1](#)). Details for the preparation and shipment of samples will be provided by the laboratory and are detailed in the laboratory manual. Reference ranges for all central laboratory safety parameters will be provided to the site.

If additional non-protocol specified laboratory assessments result in a change in subject management or are considered clinically significant by the investigator (e.g., SAE or AE of special interest or dose modification) the results must be recorded in the CRF.

Refer to the SRM/laboratory manual for appropriate processing and handling of samples to avoid duplicate and/or additional blood draws.

The following laboratory assessments will be performed: serum creatinine, HbA1c, liver function tests [AST (SGOT), ALT (SGPT), alkaline phosphatase, bilirubin, GGT], and urine and serum β hCG pregnancy test (for women of child bearing potential). All study-required laboratory assessments will be performed by a central laboratory, with the exception of HbA1c and creatinine at Screening and urine pregnancy test at Screening/Randomization.

Screening HbA1c and serum creatinine

Screening HbA1c and serum creatinine values should be based on the most recent local laboratory values taken as part of usual care within the previous 6 months and the values entered into the eCRF. These assessments must have been performed at an accredited laboratory. HbA1c screening results must be either Diabetes Control and Complications Trial (DCCT) aligned or International Federation of Clinical Chemistry and Laboratory Medicine (IFCC) standardized. HbA1c screening results from point of care equipment are acceptable provided that the equipment is maintained by an accredited laboratory. If HbA1c or creatinine have not been assessed in the previous 6 months, laboratory assessments will be performed via the central laboratory to determine eligibility (if a local laboratory is used in error the results are acceptable for determining eligibility). The investigator has the discretion to repeat screening HbA1c, and/or creatinine, based on clinical rationale even if previously available local results meet the eligibility criteria to allow the investigator to accommodate the possibility of change between screening and randomisation.

Re-screening of subjects who did not meet the eligibility criteria for HbA1c or creatinine based on local laboratory values taken as part of usual care is permitted. If values were based on laboratory results as part of usual care then one re-test is permitted within the protocol at Screening. Any future re-screening will be based on laboratory results obtained as part of usual care.

Pregnancy testing (for women of childbearing potential)

At the screening visit perform a urine pregnancy test. If the urine pregnancy test is positive, send a serum blood sample to the central laboratory for confirmation of pregnancy.

At the Randomisation visit perform a urine pregnancy test. If the result is positive do not randomize the subject. If the urine pregnancy test is negative then the subject can be randomised (provided all other eligibility criteria have been met).

If Screening and Randomisation are to take place at the same visit then follow the instructions for Screening. Do not randomise if the urine pregnancy test is positive; send a serum blood sample to the central laboratory for confirmation of pregnancy. If the urine pregnancy test is negative then the subject can be randomised at the same visit (provided all other eligibility criteria have been met).

